## 7 Trial objectives and endpoints

### Panel 3 Objectives and endpoints

Objectives	Endpoints
Primary objective	
To compare the efficacy of subcutaneous injections of brodalumab to oral administration of fumaric acid esters in subjects with moderate to severe plaque psoriasis who are naive to systemic treatment.	
Co-primary endpoints:
 
 
At least 75% improvement from baseline at Week 24 in Psoriasis Area and Severity Index (PASI)
 
Static Physician's Global Assessment (sPGA) scale score of 0 or 1 at Week 24
 
 
Secondary endpoints:
 
 
At least 90% improvement from baseline at Week 24 in PASI
 
100% improvement from baseline at Week 24 in PASI
 
Change from baseline at Week 24 in PASI score
 
PASI improvement (%) from baseline at Week 24
 
Change from baseline at Week 24 in affected body surface area (BSA)
 

Secondary objectives	
To compare the effect on patient reported outcomes of subcutaneous injections of brodalumab to oral administration of fumaric acid esters in subjects with moderate to severe plaque psoriasis.	
Secondary endpoints:
 
 
Psoriasis Symptom Inventory (PSI) responder at Week 24 (total score <math>\leq 8</math>, with no item scores <math>> 1</math>)
 
PSI total score of 0 at Week 24
 
Number of symptom-free days from randomisation to Week 24 (symptom-free day = daily total PSI of 0 on that day)
 
Burden of symptoms assessed as the normalised area under the curve (AUC) of PSI from baseline to the last available assessment
 
Change from baseline at Week 24 in Dermatology Life Quality Index (DLQI) total score
 
DLQI total score of 0 or 1 at Week 24
 

To evaluate the safety and tolerability of subcutaneous injections of brodalumab versus oral administration of fumaric acid esters in subjects with moderate to severe plaque psoriasis.	
Secondary point:
 
 
Frequency of AEs and SAEs by preferred term
 

Exploratory objective	

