##### **Secondary endpoints:**

- At least 90% improvement from baseline at Week 24 in PASI
- 100% improvement from baseline at Week 24 in PASI
- Change from baseline at Week 24 in PASI score

- PASI improvement (%) from baseline at Week 24
- Change from baseline at Week 24 in affected body surface area (BSA)
- Psoriasis Symptom Inventory (PSI) responder at Week 24 (total score  $\leq 8$ , with no item scores  $> 1$ )
- PSI total score of 0 at Week 24
- Number of symptom-free days from randomisation to Week 24 (symptom-free day = daily total PSI of 0 on that day)
- Burden of symptoms assessed as the normalised area under the curve (AUC) of PSI from baseline to the last available assessment
- Change from baseline at Week 24 in Dermatology Life Quality Index (DLQI) total score
- DLQI total score of 0 or 1 at Week 24
- Frequency of AEs and SAEs by preferred term

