### **13.3.6 Analysis of secondary efficacy endpoints**

All binary endpoints will be analysed in a similar manner as the co-primary endpoints, by analysing the difference in response rates between treatment groups using the Cochran-Mantel-Haenszel test.

Continuous endpoints like absolute PASI score, % PASI improvement, and NAPSI improvement will be modelled by MMRM to compare treatments through Week 24. The mixed model will include treatment group, week, interaction between treatment and time, baseline PASI/NAPSI score, and baseline weight group as fixed factors. Within subject covariance will be estimated by an unstructured covariance matrix (if possible).

Number of symptom-free days will be summarised.

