### **13.3.7 Analysis of patient reported outcomes**

The PROs will be summarised by treatment and stratification group. Further DLQI, change from baseline will be compared between treatments by MMRM including treatment group, week, interaction between treatment and time, baseline DLQI score and baseline weight group as fixed factors. Within subject covariance will be estimated by an unstructured covariance matrix (if possible). DLQI total score of 0 or 1 will be analysed by a Cochran-Mantel-Haenszel model adjusting for baseline weight group.

The AUC for the PSI total score will be calculated for each subject using the standard trapezoidal rule. The AUC will be normalised by dividing with the time period from baseline to the last available assessment of the PSI total score. The normalisation converts the AUC to the original scale of the PSI total score. Missing assessments of the PSI total score in-between non-missing assessments will not be imputed, which corresponds to linear interpolation between the non-missing assessments of the PSI total score. The normalised AUCs will be analysed using an analysis of covariance (ANCOVA) with treatment group, baseline weight group and the baseline PSI total score as explanatory variables.

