### **13.3.11 Handling of missing values**

Missing data for categorical endpoints will be imputed with non-responder imputation. Missing data for continuous endpoints will be dealt with by a mixed model for repeated measurements.

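### Symptom-free days are summarised by arm with no treatment difference, interval or test, and the raw count is not adjusted for diary days observed

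*Combined protocol and SAP*

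**What the plan says.** Panel 3 places symptom-free days under the secondary objective "To compare the effect on patient reported outcomes of subcutaneous injections of brodalumab to oral administration of fumaric acid esters", and Section 13.3.4 lists the endpoint among the secondary endpoints. It is a count of the days between randomisation and Week 24 on which the daily PSI total is 0.

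The only sentence on its analysis is in Section 13.3.6: "Number of symptom-free days will be summarised". Section 13.3.7 adds a general rule: "The PROs will be summarised by treatment and stratification group". Section 13.3.10 says that continuous data are described by mean, median, SD, minimum and maximum.

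The normalised PSI AUC comes from the same daily diary and is treated more fully in Section 13.3.7. For time observed: "The AUC will be normalised by dividing with the time period from baseline to the last available assessment of the PSI total score". Gaps between entries are bridged by linear interpolation. For the comparison: "The normalised AUCs will be analysed using an analysis of covariance (ANCOVA) with treatment group, baseline weight group" and baseline PSI.

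Section 13.3.11 has two general rules on missing data: "Missing data for categorical endpoints will be imputed with non-responder imputation" and "Missing data for continuous endpoints will be dealt with by a mixed model for repeated measurements".

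**The concern.** Of the six patient-reported efficacy endpoints in Panel 3, this is the only one without a formal comparison. PSI responder, PSI total 0 and DLQI 0 or 1 get a Cochran-Mantel-Haenszel test, DLQI change gets an MMRM, and PSI AUC gets an ANCOVA.

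The count also depends on how long and how completely the diary was kept. A subject can add a symptom-free day only on an evening with an entry. The PSI is completed once a day (Section 11.4.2.4), and Panel 2 has the device returned at Week 24 or at early termination, so a subject who leaves early stops adding days. Neither rule in Section 13.3.11 settles this. A mixed model cannot complete a whole-period count with one value per subject, and non-responder imputation is not stated to apply to single diary days. There is no rule for missed evenings, for days after drop-out or for minimum diary completion.

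Readers will compare the two arm means. If time observed differs, so will the means, even with equal symptom control, and no interval will show how uncertain the difference is.

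**Working it through.** The documents give no figure for symptom-free days, so there is none to reproduce. The drop-out rates come from the sample-size section, so the first step checks that the plan's power figures really rest on them.

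**1. The plan's own figures (Section 13.1, Panel 13).** Brodalumab PASI 75: 80% × (1 − 0.40) = 48%. Fumaric acid esters: 50% × (1 − 0.50) = 25%. With 102 per arm, two-sided 5%, an arcsine approximation to Fisher's exact test with continuity correction gives power 0.910, as stated. For sPGA, 60% against 37.4% gives 0.876, as stated. The product is 0.91 × 0.876 = 0.797, stated as 80%. The drop-out rates are therefore the plan's working assumptions.

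**2. Inputs.**
- Treatment period D = 168 days (Panel 2).
- Drop-out d = 0.50 for fumaric acid esters. For brodalumab the plan says less than 40%; d = 0.40 is used as the upper bound (Section 13.1).
- Assumed: on each observed day the chance of PSI 0 is p = 0.30, the same in both arms and constant over time. The ratio between arms does not depend on the value of p.
- Assumed: diary completion c, and the timing of drop-out.

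**3. Formulas.** Expected count = p × c × mean days observed. If drop-out is spread evenly over the period, mean days observed = D × (1 − d/2). If all drop-out is at day t, it is (1 − d) × D + d × t.

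**4. Drop-out alone (c = 1 in both arms).**

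| Timing (assumed) | Days, brodalumab | Days, fumaric acid esters | Expected counts | Ratio |
|---|---|---|---|---|
| Even | 168 × 0.80 = 134.4 | 168 × 0.75 = 126.0 | 40.3 v 37.8 | 1.07 |
| All at day 28 | 0.6 × 168 + 0.4 × 28 = 112.0 | 0.5 × 168 + 0.5 × 28 = 98.0 | 33.6 v 29.4 | 1.14 |
| All at day 140 | 0.6 × 168 + 0.4 × 140 = 156.8 | 0.5 × 168 + 0.5 × 140 = 154.0 | 47.0 v 46.2 | 1.02 |

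**5. Lower brodalumab drop-out.** At an assumed 10%, spread evenly: 168 × 0.95 = 159.6 days, so 47.9 v 37.8 and a ratio of 1.27.

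**6. Diary completion alone (no drop-out).** At an assumed 90% v 80%: 0.30 × 168 × 0.90 = 45.4 v 0.30 × 168 × 0.80 = 40.3, a ratio of 0.90/0.80 = 1.125, about 1.13. If completion is equal, c cancels and the ratio is 1. Combined with the even drop-out in step 4: 36.3 v 30.2, a ratio of 1.20.

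**7. Rate per completed diary day.** (p × c × days) / (c × days) = p = 0.30 in both arms in every case above. This exact equality needs p to be constant. If symptom-free days become more common later in treatment, subjects who leave early have a lower proportion even after normalisation. Normalising removes the effect of unequal time observed, but not that of informative drop-out.

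**The case against.** The strongest reply is that this was a choice. The objective to compare is served by the other patient-reported endpoints, three of them from the same diary. Symptom-free days has no part in the success criterion, and Section 13.3.10 applies no multiplicity correction, so describing one further endpoint avoids another uncorrected p-value. This stands as a reason to rate the point low. It does not explain the lack of an estimate with an interval, or of any adjustment for time observed.

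A second reply is that counting days after drop-out as not symptom-free is a defensible composite, in the spirit of the non-responder rule for the co-primary endpoints. That is right, but the plan does not state it, and it would not justify penalising a missed evening in a subject still on treatment. For the same reason, a reader should not infer that the plan has decided to treat missed evenings as symptomatic. It is silent, and the raw count merely has that effect.

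A third reply is that Section 13.3.10 foresees a statistical analysis plan update. It is not among the documents, but it is a natural place for the change.

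**Conclusion.** The point holds as a cheap improvement to a secondary endpoint. Followed as written, the plan yields a raw count per arm with no estimate of the treatment difference. On the plan's own drop-out inputs, that count favours brodalumab by a ratio of about 1.07 (1.02 to 1.14) when daily symptom control is identical. This range takes brodalumab drop-out at 40%, full diary completion and a constant daily chance of PSI 0. Lower brodalumab drop-out or poorer completion on fumaric acid esters would widen the gap; the documents give no figures for either.

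Two stronger readings are not supported. A reader might infer that the arms are not compared at all, but the summary is by treatment with a measure of spread; what is missing is a formal comparison. A reader might also infer a large bias. For example, drop-out all at Week 10 (day 70) gives 0.6 × 168 + 0.4 × 70 = 128.8 v 0.5 × 168 + 0.5 × 70 = 119.0 days, a ratio of 1.08. Adding completion of 90% v 75% multiplies this by 1.20, to 1.30. Most of that excess comes from a completion gap for which the documents give no basis.

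The sample size and co-primary analyses are untouched.

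**What to change.** Replace the sentence in Section 13.3.6 with a comparison of the proportion of completed diary days that are symptom-free. Choose one model in advance:

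- ANCOVA with treatment group, weight group and baseline PSI, matching the PSI AUC model; or
- a negative binomial model for the count, with the log of completed diary days as offset.

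Report the treatment difference or ratio with its 95% confidence interval.

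Add a sensitivity analysis of the count over the full 168 days, with missing and post-drop-out days counted as not symptom-free. Subjects with no diary entries have no proportion to analyse and count as 0 days here. This version shows what the main analysis cannot: the result when early departure is treated as failure. Report completed diary days per arm beside both.

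The cost is a few lines of text, a little more analysis work and one more uncorrected secondary p-value.

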### **13.3.7 Analysis of patient reported outcomes**

The PROs will be summarised by treatment and stratification group. Further DLQI, change from baseline will be compared between treatments by MMRM including treatment group, week, interaction between treatment and time, baseline DLQI score and baseline weight group as fixed factors. Within subject covariance will be estimated by an unstructured covariance matrix (if possible). DLQI total score of 0 or 1 will be analysed by a Cochran-Mantel-Haenszel model adjusting for baseline weight group.

The AUC for the PSI total score will be calculated for each subject using the standard trapezoidal rule. The AUC will be normalised by dividing with the time period from baseline to the last available assessment of the PSI total score. The normalisation converts the AUC to the original scale of the PSI total score. Missing assessments of the PSI total score in-between non-missing assessments will not be imputed, which corresponds to linear interpolation between the non-missing assessments of the PSI total score. The normalised AUCs will be analysed using an analysis of covariance (ANCOVA) with treatment group, baseline weight group and the baseline PSI total score as explanatory variables.

### **13.3.8 Analysis of safety**

The analysis of safety will be based on the safety analysis set.

### 13.3.8.1 Adverse events

AEs will be coded during the trial according to the most recent version of Medical Dictionary for Regulatory Activities (MedDRA). All AEs will be presented by preferred terms (PT) and primary system organ class (SOC).

Treatment-emergent AEs (TEAEs) will be summarised, however, all AEs recorded during the course of the trial will be included in the subject data listings. An event will be considered treatment-emergent if started on or after the first day of IMP and no later than 5 half-lives after the last day on randomised treatment, or if started before the first use of IMP and worsened in severity thereafter. The tabulations described in the following will only include the treatment-emergent events.

An overall summary of the number of subjects with any TEAEs, the percentage of subjects with at least one event, the number of events and the event rate per 100 years will be presented. These summaries are done by SAEs, discontinuations from the trial due to AEs, treatment-related AEs, severe AEs, relation to device, outcome and AESIs.

Where there are several recordings of a specific AE within a subject, severity will be taken as the most severe recording for that specific AE. If a subject experience more than one AE of the same type, all severity evaluations should be recorded.

Where there are several recordings of causal relationship to a specific AE within a subject, causal relationship will be taken as the most-related recording from the last report of that AE.

Related AEs are defined as AEs for which the (sub)investigator has not described the causal relationship to IMP as 'not related'.

Summary tables based on SOC and PT are made for all TEAEs, serious TEAEs, related AEs, severe TEAEs, TEAEs reported as AESIs, AEs leading to withdrawal, and TEAEs with preferred term that are experienced by at least 5% of the subjects in any treatment arm or by at least 5% of all subjects.

Finally, relevant AE listings will be created.

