### 10.2 Administration of investigational medicinal products

The IWRS system will assign the required kits numbers for each subject at each dispensing visit.

The first day of dosing is defined as Day 0 (baseline visit).

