### Fumaric acid esters

Fumaric acid esters tablets will be administered orally at home following the dose scheme in [Panel 6](#). The first dose should be taken in the evening at day of the baseline visit (Day 0, visit 2).

NOTE: The last tablet of fumaric acid esters initial (30 mg dimethyl fumarate tablets) should be taken in the evening of Day 19. Hereafter, the regimen must be shifted to fumaric acid esters, 120 mg dimethyl fumarate tablets, starting with 1 tablet once daily in the evening from Day 20 to Day 27 (Week 3 regimen, see [Panel 6](#)).

Each subject will only receive one package of Fumaderm® Initial and this package will be used to up-titrate the subject to tolerate Fumaderm®, for which individual dosing can be performed. Experience has shown that the initial therapeutic effects with fumaric acid esters can be expected from Week 4 to Week 6 (see SmPC for Fumaderm®).

The maximum daily dosage of 3×2 tablets must not be exceeded, and in many cases, administration of the maximum daily dose is not required as maintenance dose.

The fumaric acid esters are gastro-resistant tablets and must be swallowed whole with plenty of liquid, during or immediately after meals. Generally, it is important to ensure that enough liquid is drunk over the course of the day (1½ to 2 litres).

TRIAL ID: LP0160-1327	DATE: 17-APR-2018	VERSION: 4.0 PAGE 45 OF 108
-----------------------	-------------------	--------------------------------

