## 11.6 Other safety assessments

### 11.6.1 Laboratory testing

#### 11.6.1.1 Safety laboratory blood analysis

Blood samples will be drawn for analysis of laboratory parameters according to the schedule of trial procedures ([Panel 2](#)).

The following blood sample tests will be analysed at central laboratory: serum chemistry, haematology, serum pregnancy, urinalysis (incl. urine pregnancy tests).

The central laboratory will provide a trial specific laboratory manual that outlines handling, labelling, and shipping procedures for all samples. All blood samples will be obtained by venepuncture before IMP administration. The date and time of sample collection will be recorded in the source documents at the site.

The serum chemistry, haematology and other tests are listed below:

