## **12.2 Reporting of adverse events**

AEs reported by the subject or observed by the (sub)investigator must be recorded on the AE form of the eCRF and should be described in the following manner:

The *AE term* will be in precise English medical terminology (i.e. not necessarily the exact words used by the subject). Whenever possible, a specific diagnosis should be stated (for example allergic contact dermatitis).

The *duration* of the AE must be reported by the start date and stop date of the event. In addition, it must be recorded whether the AE started prior to start of IMP.

AEs must be classified in terms of severity, causality and outcome according to the definitions in [Appendix 3: Classification of adverse events](#).

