### **13.3.10 General principles**

All statistical analyses of efficacy endpoints will be based on the FAS and safety endpoints on the safety analysis set (SAS). All significance tests will be two-sided using the 5% significance level. All CIs will be presented with 95% degree of confidence. No corrections for multiplicity will be performed.

If not mentioned otherwise, endpoints will be summarised descriptively at each visit by treatment and in total.

An observed-cases approach will be used for tabulations of data by visit (i.e. involving only those subjects who attended each specific visit). For categorical endpoints number of subjects not attending each specific visit will also be added.

Categorical data will be summarised using the number and percentage of subjects in each category. Continuous data will be summarised using the mean, median, SD, minimum, and maximum values.

In general, for endpoints evaluated as change from baseline and/or where a baseline adjustment is applied, baseline is defined as information collected at the randomisation visit (Visit 2), if not otherwise stated. If the assessment is not available at the randomisation visit but at the screening visit (Visit 1) then this will be used instead.

All the analyses specified in the protocol will be reviewed in relation to the blinded data obtained and the statistical analysis plan update will be finalised before breaking the randomisation code.

Any changes from the statistical analysis planned in this clinical trial protocol will be described and justified in the statistical analysis plan update (SAPU) and/or in the clinical trial report dependent on the type of deviation.

For endpoints evaluated over time, plots will be made to explore the trajectory with time.

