***Principles for data entry***

Clinically significant abnormal findings at the (first) screening visit will be documented as medical history in the eCRF.

If an abnormal finding (vital signs, physical examination, laboratory tests) at any other visit than the (first) screening visit is considered by the investigator to be clinically significant, it will be reported as an AE in accordance with Section 12.2. Further, any clinically significant deterioration of a pre-existing condition as well as any new clinically significant sign, symptom or illness observed after screening will be reported as an AE in accordance with Section 12.2.

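### Adverse events that start on Day 0 before the first dose count as treatment-emergent even if they never worsen

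*Combined protocol and SAP*

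**What the plan says.** Section 13.3.8.1 gives two routes to treatment-emergent status. The first is by day: "An event will be considered treatment-emergent if started on or after the first day of IMP", up to 5 half-lives after the last day on treatment. The second is by use: "or if started before the first use of IMP and worsened in severity thereafter". The AE tabulations are limited to treatment-emergent events, while the listings hold all AEs.

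The first dosing day coincides with the baseline visit. Section 10.2 states: "The first day of dosing is defined as Day 0 (baseline visit". For fumaric acid esters, section 10.2.1 adds: "The first dose should be taken in the evening at day of the baseline visit". Brodalumab is given at the site during that visit, under supervision (section 10.2.1).

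Visit 2 is also the analysis baseline. Section 13.3.10 says that "baseline is defined as information collected at the randomisation visit (Visit 2", with screening values as the fallback. Section 11.6.1.1 says: "All blood samples will be obtained by venepuncture before IMP administration".

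On reporting, Appendix 4D (Principles for data entry) makes a finding an AE when an abnormality "at any other visit than the (first) screening visit is considered by the investigator to be clinically significant". Sections 11.5.1, 11.5.2 and 11.6.1.1 repeat the rule for vital signs, physical examination and laboratory results. Only screening findings go to medical history instead. Section 12.2 requires a start date for each AE and then: "In addition, it must be recorded whether the AE started prior to start of IMP".

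**The concern.** Taken together, these provisions make a pre-dose finding at Visit 2 a reportable AE with a Day 0 start date, and the calendar-day limb then makes it treatment-emergent. The same value can appear as the pre-treatment baseline in the shift tables of sections 13.3.8.3 and 13.3.8.4 and as an on-treatment event in the AE tables.

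The definition also disagrees with itself. An event on Day 0 before dosing meets the first limb because of its date. It would fail the second unless it worsened. The limbs are joined by an alternative, so the first prevails, although the second indicates that pre-dose events were meant to count only on worsening.

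At stake is the accuracy of the AE and SAE frequencies by preferred term, a listed secondary endpoint (Panel 3 and section 13.3.4). The efficacy analyses do not use this definition.

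**Working it through.** The plan states no figure to reproduce here, because the point concerns a classification rule. The check has two parts.

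**1. The rule, case by case.** The inputs are the two limbs in section 13.3.8.1 and Day 0 as first dosing day in section 10.2.

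- As written: treatment-emergent if onset day ≥ 0, or if onset is before first use and the event worsened.
- Anchored on first use: treatment-emergent if onset is at or after first use, or if onset is before first use and the event worsened.

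| Onset | Worsened after first dose | As written | Anchored on first use |
|---|---|---|---|
| Day −1 | no | no | no |
| Day −1 | yes | yes | yes |
| Day 0, before dose | no | **yes** | **no** |
| Day 0, before dose | yes | yes | yes |
| Day 0, after dose | either | yes | yes |
| Day 1 | either | yes | yes |

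Exactly one case differs: onset on Day 0 before the first dose, without worsening. Re-anchoring loses no event that worsens. It is kept by the second limb, and Appendix 3 also requires a new AE record when severity increases.

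**2. The size.** The inputs are 102 subjects per arm (section 13.1) and the 5% threshold for the common-event table (section 13.3.8.1). I assume that the safety set is close to 102 per arm.

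- One subject: 1/102 = 0.98 percentage points for a preferred term.
- 5% of an arm: 0.05 × 102 = 5.1, so 6 subjects are needed for a term to enter the table through one arm.
- The documents give no rate of clinically significant pre-dose findings at Visit 2. Assumed rates of 1%, 2% and 5% give 102 × 0.01 = 1.02, 102 × 0.02 = 2.04 and 102 × 0.05 = 5.1 subjects per arm, over all preferred terms together.

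Even at the assumed 5%, with every finding coded to one term, the expected 5.1 is below 6. These events would not be expected to bring a term into the table by themselves, though they could tip one already near the threshold.

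**The case against.** The strongest defence is that a calendar-day rule is conservative. AE timing is collected as dates, and the rule guarantees that same-day reactions to the first injection are counted. The alternative relies on an item completed by an unblinded investigator and, for fumaric acid esters, on an unobserved evening dose at home. This has some force, and the fix should keep unclear cases as treatment-emergent. It does not justify ignoring the item where it is clearly completed, since the trial collects it and no analysis section uses it.

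The affected group is also small. Exclusion criteria 6 and 7 remove clinically significant or specified laboratory abnormalities at screening, at most 28 days earlier. Criteria 5 and 24 can remove significant conditions seen when eligibility is re-checked at baseline. This stands, but does not empty the group: criteria 6 and 7 refer to screening values, and section 8.1 confirms laboratory eligibility on the screening samples.

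Three stronger readings may tempt a reader, and the documents do not support them.

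- Every abnormal baseline finding becomes a treatment-emergent AE. In fact it must be judged clinically significant, be reported as an AE and be dated Day 0. One dated earlier falls under the second limb.
- All Visit 2 assessments are pre-dose in both arms. Section 11.6.1.1 fixes only blood sampling before dosing. For fumaric acid esters the evening dose puts the whole visit before it, but nothing says that vital signs and examination precede the on-site brodalumab injection.
- The comparison between arms is materially biased. The pre-dose part of Day 0 is longer for fumaric acid esters, but only by hours on one day. Randomisation makes pre-dose findings similar in expectation, and no hypothesis test on AEs is described.

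**Conclusion.** The point holds in a limited form. As written, the definition counts a pre-dose Day 0 AE that never worsens as treatment-emergent, contrary to its own second limb, and leaves unused the eCRF item that would separate such events.

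The size is probably small: about 1 percentage point of an arm per affected subject, with the number of subjects unknown. The 1–5% range is an assumption. Efficacy is not affected, and between-arm risk differences are largely unaffected.

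The conclusion rests on two further assumptions. First, vital signs, examination and laboratory tests are done at Visit 2. The safety rows of Panel 2 are not in the text available to me, so this is inferred from the change-from-baseline analyses in sections 13.3.8.3 and 13.3.8.4 and the baseline definition in section 13.3.10. Second, a finding is dated to the day of the visit or sample. The severity is minor.

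**What to change.** In section 13.3.8.1, or in the statistical analysis plan update that section 13.3.10 provides for:

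- Anchor the first limb on first use of IMP instead of the first day of IMP, so that both limbs share one reference point.
- For AEs dated on the day of first dose, use the existing eCRF item on onset before IMP. Events marked as starting before IMP count only if they worsen afterwards.
- Keep events with the item missing or unclear as treatment-emergent.

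The cost is a sentence or two of text and a small programming change. The item is already collected, so no new data are needed, although a short reminder to sites on completing it for Visit 2 findings would help. The downside is a small reliance on an investigator-completed item in an open-label trial. All AEs remain in the listings, so any reclassified event can still be seen.
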